#### **b. Procedure Risks**

New patients will not be exposed to any additional research procedures outside the standard of care. For return patients they will undergo a simple uterine biopsy that they will have the knowledge ahead of time about as they have already undergone the same procedure previously. For the healthy controls they will undergo one minor procedure any may benefit from the testing in the future. The endometrial biopsy in general is a low risk procedure with a risk of complications of less than 1 in 1,000 with the most common side

effects of short lived (lasting a few minutes at most) of mild cramping and mild spotting

**Use of Deception in the Study**

Deception will not be used.

---

**d. Use of Audio and Video Recordings**

There will be no audio or video recording.

---

**e. Alternative Procedures or Courses of Treatment**

For unexplained recurrent pregnancy loss and unexplained infertility patients there is no standard of care treatment. Empirical treatment includes supplementing with progesterone in a subsequent pregnancy started in the luteal phase or with the first pregnancy test however there is little evidence based medicine behind these options. At most this would be a 1-2 month delay of starting this empiric treatment for patients who fall in the abnormal group who had the option for treatment with progesterone or antibiotics/probiotics and subsequent biopsy.

Another option we review with our recurrent pregnancy loss patients is in vitro fertilization with PGS (pre-implantation genetic screening) however this has not been shown to improve time to live birth and is very expensive. Again if patients decided to have this treatment the study would only again delay this by 1-2 months and have no effect on the patient's success rate of the treatment itself given a minor time delay. Furthermore it may allow us to better time an embryo transfer for these patients as ERA has been used to identify the best window of implantation after IVF.

For unexplained infertility treatments include oral fertility medications (clomid) plus insemination cycles or in-vitro fertilization cycles. Again this would be at most a 1-2 month delay which we do not anticipate would change their overall prognosis or outcome for pregnancy. Again if patients proceed to IVF and embryo transfer the knowledge from the study could be used to better time an embryo transfer.

For the healthy controls there is at least a 1-2 month set up to proceed with egg harvesting. The biopsy would be done during this set up time and would not cause a clinically significant delay.

---

**f. Will it be possible to continue the more (most) appropriate therapy for the participant(s) after the conclusion of the study?**

As there is no standard treatment of unexplained recurrent pregnancy loss, all therapy as described above will be possible for these patients. For unexplained infertility the standard appropriate therapy will resume after the conclusion of the study.

---

**g. Study Endpoint(s)**

For patients who are found to have a receptive endometrium, the study end point will be after the standard medical evaluation as described. For patients who are found to have a non receptive endometrium or abnormal microbiome the study end point will be after the second endometrium biopsy. Participants will be allowed to continue any standard

medically indicated treatments throughout the study. For healthy controls the study end point will be after the first endometrial biopsy and we will not plan a repeat biopsy. The study will end once the anticipated total number of participants is met to complete an adequate power analysis.

---

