### **a. Procedures**

Patients enrolled in the study will be those presenting to the clinic for evaluation and treatment of recurrent pregnancy loss and infertility. Healthy controls will be patients presenting for elective egg freezing and elective sex selection and recruited from the general population by way of flier.

Recurrent pregnancy loss and infertility patients will undergo the routine clinical standard evaluation including a uterine cavity evaluation, evaluation for endometritis, ovarian reserve testing, and for patients with recurrent pregnancy loss also parental chromosome analysis, antiphospholipid antibody blood testing and thyroid screening. Egg freezing patients will undergo routine clinical evaluation which includes uterine ultrasound evaluation and ovarian reserve testing and elective sex selection patients will undergo a routine evaluation which includes a uterine cavity evaluation, ovarian reserve testing and blood testing.

For new patients presenting with no prior evaluation we will perform the uterine cavity evaluation as per standard of care in the follicular phase of the menstrual cycle. The endometrial biopsy is typically done during this same appointment however the endometrial biopsy will be deferred for the purposes of the study in order to perform the endometrial biopsy during the window of implantation after ovulation. This endometrial biopsy will be sent to pathology to rule out endometritis as per clinical standard of care and will allow us to evaluate endometrial gene expression during the window of implantation. The endometrial sample will be sent to Ivigen for an endometrial receptivity array (ERA) and microbiome analysis at no extra cost to the patient. The ERA provides information on the receptivity of a patient's endometrium to the implantation of an embryo. It is hypothesized that unexplained recurrent pregnancy loss and unexplained infertility patients are more likely to have a nonreceptive endometrium than healthy historic controls.

For return patients with prior standard evaluation they will be invited to participate in the study. These patients will undergo an endometrial biopsy as above. The endometrial sample will be sent to Ivigen to our collaborators ([name]) for an endometrial receptivity array (ERA) and microbiome analysis at no extra cost to the patient. [name] group will perform the analysis of the sample.

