For patients whose ERA shows a non receptive endometrium in the subsequent menstrual cycle, vaginal progesterone medication which is often prescribed empirically for recurrent pregnancy loss will be prescribed to start 3 days after ovulation detected by home urine LH kits. A second endometrial biopsy will be sent for a repeat ERA at not

extra cost to the patient. The patient will still be able to participate in the study if they decline this second biopsy.

For patients who microbiome is altered, a 2 week course of oral doxycycline will be prescribed followed by 2 weeks of over the counter vaginal probiotics. A second endometrial biopsy will be sent for a repeat microbiome at not extra cost to the patient. The patient will still be able to participate in the study if they decline this second biopsy.

If on the first biopsy there is endometritis the patient will first be treated based on standard of care practice with routine use of oral antibiotics prior to undergoing a second endometrial biopsy which is also routine practice. If the microbiome or ERA is also abnormal (It would be for example EXPECTED that the microbiome will be altered in all endometritis patients) for an abnormal ERA- vaginal progesterone would be added prior to rebiopsy and/or vaginal probiotics would be added.

The patients' follow up visits and treatment regimens will be determined by the treating physician according to the standard of care treatment of recurrent pregnancy loss, unexplained infertility or other medical comorbidities.

These patients are not required to consent to any additional testing or drug treatments outside of that which is standard treatment of their condition(s). They will consent to follow up communication (phone call or email) for up to 5 years after enrollment in the study to allow for completion of data collection and pregnancy outcomes except for the healthy controls who will be followed for 1 year.

The only procedures which would be considered entirely research would be sending the endometrial biopsy tissue for ERA testing (currently endometrial biopsy is a standard of care for recurrent pregnancy loss and unexplained infertility) however this is not sent for ERA testing.

Empiric use of vaginal progesterone is often used in the setting of recurrent pregnancy loss and unexplained fertility however doing a repeat biopsy in this setting would be considered research- not standard of care.

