#### a. Past Experimental and/or Clinical Findings

Recurrent pregnancy loss is a difficult clinical diagnoses defined as when women have >2 unexplained miscarriages (not accounted for by genetically abnormal fetal tissue) <10 weeks. After a full evaluation for genetic, endocrine, anatomic, immunologic, infectious and autoimmune conditions, the majority of cases remain unexplained. In unexplained infertility normal sperm, normal ovulatory function and patent fallopian tubes are documented and the reason for infertility remains unexplained. The role of endometrial factors in pregnancy loss and unexplained infertility is becoming of increasing interest. Studies have identified differences in the endometrium in protein expression and endometrial glandular development in women with unexplained recurrent pregnancy loss. Some studies have suggested that luteal phase progesterone may change the endometrial environment. Therefore the purpose of this study was to look at a more comprehensive genetic expression profile and the microbiome atmosphere during the window of implantation and to evaluate if luteal phase progesterone support normalizes this genetic expression profile for RPL patients who are found to have non- receptive endometrial biopsies. Understanding the genetic expression profile of the endometrium and the microbiome atmosphere during the window of implantation for unexplained infertility may help identify a previously unknown uterine factor in unexplained infertility. Prior studies have shown that a non receptive ERA and an abnormal microbiome (lactobacilli non dominant) is associated with decreased implantation rate, pregnancy rate and live birth rates in women undergoing IVF.

---

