**h. Eligibility Criteria**

i. Inclusion Criteria

Subjects must fulfill the following inclusion criteria to be eligible to participate in the study:

1. Have a diagnosis of recurrent pregnancy loss as defined as two or more unexplained pregnancy losses at less than 10 weeks (miscarriages with known chromosomal errors excluded) OR have a diagnosis of unexplained infertility defined as normal ovarian reserve testing, normal ovulatory function, normal semen analysis defined why WHO criteria and evidence of at least one patent fallopian tube.
2. Agree to the standard of care testing for evaluation of recurrent pregnancy loss OR unexplained infertility OR routine testing for preparation for oocyte freezing or elective sex selection.
3. Be at least 18 years old and less than 46 years old.
4. Have menstrual cycles that occur in 25-35 day intervals
5. Agree to follow up for 5 years from the date of enrollment

ii. Exclusion Criteria

1. Irregular menstrual cycles
2. Presence of untreated submucosal fibroids or polyps
3. an unligated hydrosalpinx
4. non-ovulatory progesterone level on the day of endometrial biopsy
5. Women <21 or >45 years old.

---

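### With no antibiotic-free interval before the first biopsy, a return patient's baseline microbiome sample may be taken during or soon after antibiotics

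*Protocol*

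**What the plan says.** Section 2g (Study Endpoint(s)) governs concomitant treatment in one sentence, which runs over a page break: "Participants will be allowed to continue any standard" and then "medically indicated treatments throughout the study". No agent is excepted and no period is carved out.

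Section 7h (Eligibility Criteria) lists five exclusions. None concerns current or recent use of antibiotics, progesterone or vaginal probiotics. The only one that mentions progesterone is "non-ovulatory progesterone level on the day of endometrial biopsy". It removes women whose level is too low, not women taking the drug.

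Section 2a (Procedures) describes two ways in. New patients have their clinical biopsy moved to the window of implantation, so for them the biopsy precedes treatment. The other group has been worked up already: "For return patients with prior standard evaluation they will be invited to participate in the study". Section 2b (Procedure Risks) says of these women that they know what to expect, "as they have already undergone the same procedure previously".

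Section 2a also states that patients undergo a "routine clinical standard evaluation including a uterine cavity evaluation, evaluation for endometritis", and that a woman with endometritis is "treated based on standard of care practice with routine use of oral antibiotics". It adds that antibiotics are often given for non-specific findings. Section 8e says the clinic uses both oral doxycycline and vaginal progesterone routinely in many of its patients.

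**The concern.** The first biopsy does three jobs. It supplies the patient-control comparison, it is the baseline for the before-after comparison, and it decides who is offered progesterone or doxycycline followed by probiotics. A sample taken under the influence of one of these agents does none of them cleanly.

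The protocol itself gives reason to think the agents may matter. Section 3a says: "Some studies have suggested that luteal phase progesterone may change the endometrial environment". The study also sets out to learn whether antibiotics followed by probiotics improve an altered microbiome. If some patients' first samples already reflect recent antibiotics, the patient group's rate of abnormal results is not the untreated rate, and a later change from that baseline is hard to interpret.

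Permitted medication and treatment-free intervals are fixed in a protocol. An analysis plan can set exposed samples aside only if the agent and date were captured, and this protocol does not ask for them. Section 8e provides for tracking side effects, not prior use.

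**Working it through.** **Step 1: is there a route to exposure before the first biopsy?**

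- *Antibiotics, return patients: yes.* The standard work-up looks for endometritis (2a). Return patients have had the biopsy before (2b). Endometritis, and often non-specific findings, lead to antibiotics (2a), and doxycycline is routine at this clinic (8e). The woman is then invited and biopsied with no interval stated (2a, 7h). The rule in 2a for endometritis found at the first study biopsy governs what follows that biopsy, not earlier courses.
- *Progesterone: possible, but weaker.* It is in routine use (8e) and not barred (2g, 7h). However, section 2e speaks of a delay in starting empiric treatment, which suggests it has usually not begun.
- *Vaginal probiotics: no usual-care route described.* They are over the counter and no rule bars them, but the text goes no further.
- *Controls.* Section 2a lists no endometritis evaluation for egg-freezing or sex-selection women, so the antibiotic route above is specific to patients. That does not show controls to be unexposed; some are recruited by flier and no rule covers them either.

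**Step 2: does other text close the gap?** The 1-2 month delay of progesterone or antibiotics in 2e concerns patients already found abnormal, so it comes after the first biopsy. Section 2f says infertility therapy resumes when the study ends. This implies a pause, but gives no interval before the biopsy and sits awkwardly beside 2g.

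**Step 3: scale.** The protocol has no figure to reproduce; it gives neither the number of return patients nor the number treated. Only the group size of 100 comes from it (7a). All other inputs are assumptions: p = true abnormal rate, 20% to 40%; x = share of the group exposed; e = share of exposed abnormal results turned normal; h = share of exposed normal results turned abnormal; exposure unrelated to abnormality; controls unexposed.

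Observed abnormal rate = p − x·p·e + x·(1 − p)·h.

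Normalisation only (h = 0): the relative fall is x·e for any p, and the hidden results per 100 women are 100·p·x·e.

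| x | e | x·e | hidden at p = 20% | hidden at p = 40% |
|---|---|---|---|---|
| 5% | 25% | 1.25% | 0.25 | 0.5 |
| 10% | 50% | 5% | 1 | 2 |
| 20% | 75% | 15% | 3 | 6 |

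Disturbance only (e = 0, h = 25%, x = 10%): added abnormal results per 100 women = 100·x·(1 − p)·h. At p = 20% this is 100 × 0.10 × 0.80 × 0.25 = 2.0; at p = 40% it is 100 × 0.10 × 0.60 × 0.25 = 1.5. The sign is reversed and the size similar.

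If exposure is concentrated in women who were abnormal, the normalisation case grows. Section 2a expects an altered microbiome in all endometritis patients. If every exposed woman had been abnormal, x = 10% and e = 50% would hide 100 × 0.10 × 0.50 = 5 results.

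**Step 4: before-after comparison.** Suppose earlier exposure works as well as the study regimen (share e), and exposed women who are still abnormal do not respond again. Of the p(1 − x·e) women abnormal at baseline, p·e(1 − x) normalise, so the observed share is e(1 − x)/(1 − x·e). With e = 50%: 0.45/0.95 = 47.4% at x = 10%, and 0.40/0.90 = 44.4% at x = 20%. Assuming no second response is an extreme case.

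With x = 0, or e = h = 0, every shift is zero.

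**The case against.** A reader might infer that all three agents contaminate the baseline, and that abnormal results are therefore masked in patients but not in controls. The documents do not support that stronger reading.

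- Section 2e says there is no standard treatment for these diagnoses and presents progesterone as empirical and not yet started. Reading 2g as a licence for luteal progesterone in the first-biopsy cycle is possible but not the natural reading. This largely stands; progesterone is a secondary point.
- No section describes vaginal probiotics as prior usual care. This stands; probiotics belong in the record but are not part of the problem shown.
- The study regimen is antibiotics followed by probiotics, whereas the usual-care exposure is antibiotics alone. Section 3a describes an abnormal microbiome as one in which lactobacilli are not dominant, and nothing in the protocol says an antibiotic alone restores them. It might do nothing lasting, or raise the abnormal rate. This stands, so no direction can be claimed.
- A woman cured well before the study biopsy and now normal is not misclassified. This also stands; the issue is a sample taken while a drug effect may persist, which is why an interval matters.
- The protocol does not say that treatment history goes unrecorded, and the choice of analysis set can be left to an analysis plan. Both are fair. Neither supplies the interval, nor the requirement to collect dates on which such an analysis would depend.

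**Conclusion.** The point holds for antibiotics in return patients, and to a lesser extent for luteal progesterone. Sections 2g and 7h, followed as written, allow the baseline microbiome sample to be taken during or soon after an antibiotic course, and nothing in 2a, 2e or 2f prevents it. Both the patient-control comparison and the before-after baseline can be distorted.

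Neither direction nor size follows from the protocol, and the effect may be nil if few return patients were recently treated or if antibiotics alone leave no trace. Under the assumed middle case (10% exposed, half normalised, exposure unrelated to abnormality), 1 to 2 results per 100 women are hidden and a true 50% normalisation reads as 47%. Other equally assumed inputs give more, less or the opposite sign. It should be corrected because the sample is central and the correction cheap, not because a large bias has been shown.

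**What to change.** Amend 2g and 7h so that the first biopsy is taken in a cycle without supplemental progesterone and after a stated antibiotic-free interval. The investigators should set that interval; at least one full menstrual cycle is an example. Where a woman needs treatment, defer the biopsy, not the treatment. Bring 2e and 2f into line with 2g.

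Record the agent and last date of use of progesterone, antibiotics and vaginal probiotics before each biopsy, in all three groups. Report the patient-control and before-after comparisons with and without exposed first biopsies.

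The cost is a wording change, one extra data field per biopsy and a short delay for some return patients. Setting exposed biopsies aside may introduce slight selection, since treated return patients may differ from untreated ones; reporting both results shows how much that matters. If exposure proves rare, the record will demonstrate a clean baseline.

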### 3. BACKGROUND

---

#### a. Past Experimental and/or Clinical Findings

Recurrent pregnancy loss is a difficult clinical diagnoses defined as when women have >2 unexplained miscarriages (not accounted for by genetically abnormal fetal tissue) <10 weeks. After a full evaluation for genetic, endocrine, anatomic, immunologic, infectious and autoimmune conditions, the majority of cases remain unexplained. In unexplained infertility normal sperm, normal ovulatory function and patent fallopian tubes are documented and the reason for infertility remains unexplained. The role of endometrial factors in pregnancy loss and unexplained infertility is becoming of increasing interest. Studies have identified differences in the endometrium in protein expression and endometrial glandular development in women with unexplained recurrent pregnancy loss. Some studies have suggested that luteal phase progesterone may change the endometrial environment. Therefore the purpose of this study was to look at a more comprehensive genetic expression profile and the microbiome atmosphere during the window of implantation and to evaluate if luteal phase progesterone support normalizes this genetic expression profile for RPL patients who are found to have non- receptive endometrial biopsies. Understanding the genetic expression profile of the endometrium and the microbiome atmosphere during the window of implantation for unexplained infertility may help identify a previously unknown uterine factor in unexplained infertility. Prior studies have shown that a non receptive ERA and an abnormal microbiome (lactobacilli non dominant) is associated with decreased implantation rate, pregnancy rate and live birth rates in women undergoing IVF.

---

#### b. Findings from Past Animal Experiments

None

---

### 4. DEVICES USED IN THE STUDY

---

#### a. IDE-Exempt Devices

IND-Exempt Device 1	
Name:	ERA: Endometrial receptivity array (IVIGEN)
Description:	The ERA is a diagnostic tool used to evaluate the endometrial receptivity of a patient that determines whether or not an embryo is capable of implanting in the uterus.
IND-Exempt Device 2	
Name:	Vaginal progesterone (endometrin) (Ferring Pharmaceuticals Inc.)
Description:	Vaginal progesterone supplementation
IND-Exempt Device 3	
Name:	Doxycycline (Generic)
Description:	Doxycycline

---

## 5. DRUGS, BIOLOGICS, REAGENTS, OR CHEMICALS USED IN THE STUDY

---

### a. Commercial Drugs, Biologics, Reagents, or Chemicals

Commercial Product 1	
Name:	PurFem priobiotic (Bifodan A/S)
Dosage:	Dispense 1 capsule per vagina daily x 10 days
New and different use? (Y/N)	No
Commercial Product 2	
Name:	Probaclac Vaginal Probiotic (Nicar Laboratories)
Dosage:	apply 1 vaginal capsule oer vagina daily x 14 days
New and different use? (Y/N)	No
Commercial Product 3	
Name:	Lactogyn (JADRAN-GALENSKI LABORATORIJ d.d. JGL d.d)
Dosage:	1 application to vagina per day
New and different use? (Y/N)	No

---

## 6. DISINFECTION PROCEDURES FOR MEDICAL EQUIPMENT USED ON BOTH HUMANS AND ANIMALS

N/A

---

